4. To evaluate the efficacy of BAN2401 compared to placebo on CSF biomarkers ($A\beta$ [1-42], t-tau, and p-tau) at 12 months of treatment in subjects with EAD (revised per Amendment 10)

To evaluate the effects of BAN2401 compared to placebo on total hippocampal atrophy as measured by vMRI at 6 and 12 months, and left and right hippocampus, whole brain and total ventricular volume as measured by vMRI at 6, 12, and 18 months of treatment in subjects with EAD (revised per Amendment 10)

Exploratory Objectives:

1. To evaluate the effects of BAN2401 compared to placebo on clinical status in subjects with EAD by assessment ADCOMS, ADAS-Cog, CDR-SB, MMSE and FAQ at time points not listed in Key Secondary and Secondary objectives (revised per Amendment 10)
2. To explore the relationship between change from baseline in clinical status at 12 and 18 months of treatment and baseline brain amyloid pathophysiology in subjects with EAD as measured by amyloid PET (revised per Amendment 10)
3. To explore the relationship between change from baseline in clinical status and change from baseline in brain amyloid pathophysiology at 12 and 18 months of treatment in subjects with EAD as measured by amyloid PET (revised per Amendment 10)
4. To explore efficacy of BAN2401 compared to placebo and the overall study population on the ADCOMS across all clinical assessment time points in Japanese subjects with EAD (revised per Amendments 07 and 10)
5. To characterize the population pharmacokinetics (PK) of BAN2401 in EAD subjects, and to examine the effect of intrinsic and extrinsic factors on the PK (revised per Amendment 08)

EXTENSION PHASE PART A (REVISED PER AMENDMENTS 08, 11, 16, AND 19)

Primary Objective

To evaluate the long-term safety and tolerability of BAN2401 in subjects with EAD

Secondary Objective

To assess if the treatment benefit in brain amyloid levels (as measured by amyloid PET) at the end of the Core Study will be maintained over time in the Extension Phase Part A in subjects with EAD

Exploratory Objectives

1. To evaluate the clinical effects of BAN2401 in subjects with EAD on the ADCOMS, CDR-SB, ADAS-Cog, and MMSE over time during the Extension Phase Part A
2. To assess time to disease progression as evaluated by Clinical Dementia Rating (CDR) global score during the Extension Phase Part A

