9.1.3 Extension Phase

Extension Phase Part A

The Extension Phase Part A will be initiated following the Core Study to allow subjects to receive open-label BAN2401 10 mg/kg biweekly (or if the subject chooses to enter the Dosing Regimen substudy, 1 of the 2 alternative dosing regimens (either BAN2401 10 mg/kg once every 4 weeks [Q4W] or BAN2401 10 mg/kg once every 3 months [Q3M]) for up to 60 months (5 years), until the drug is commercially available in the country where the subject resides, or in the cases where drug is not yet commercially available, treatment will continue until the benefit-to-risk ratio from treatment with BAN2401 is no longer considered favorable, whichever comes first. Any subject who completed study treatment (Visit 42 [Week 79] of the Core Study) and fulfills the Extension Phase Part A inclusion and exclusion criteria ([Appendix 4](#)) will have the option to participate. Subjects who previously completed the Core Study (through the Follow-Up Visit, Visit 43) at any time before implementation of the Extension Phase Part A and/or fulfill the Extension Phase Part A inclusion and exclusion criteria ([Appendix 4](#)) will also be eligible to participate. Subjects who discontinued the Core Study will be eligible to participate in the Extension Phase Part A, provided they meet the inclusion and exclusion criteria for the Extension Phase Part A. (revised per Amendments 11, 15, 17, and 19)

All subjects will receive the BAN2401 10 mg/kg biweekly dose (or Q4W or Q3M if enrolled in the Dosing Regimen substudy) during Part A of the Extension Phase, including subjects who are confirmed *APOE4* positive (hetero- or homozygous). (revised per Amendment 19). All infusions will take place in the clinic; however, if approved by the Sponsor and allowable and conducted according to country and local guidelines, subjects will be offered the option of home infusions for approved visits. Home infusions are being implemented as a result of the Coronavirus Disease 2019 (COVID-19) pandemic to allow subjects who cannot visit clinical sites for various reasons to continue receiving treatment. Home infusions will be allowed per Sponsor approval according to country and local guidelines during the COVID-19 pandemic and following its resolution, where permitted. (revised per Amendment 14)

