- The **OLE Safety Analysis Set** is the group of subjects who receive at least 1 dose of study drug during the Extension Phase Part A. This analysis set is the analysis population used for all safety analyses which will be based on the as-treated principle. (revised per Amendments 17 and 19)
- The **OLE PK Analysis Set** is the group of subjects with at least 1 quantifiable BAN2401 serum concentration with a documented dosing history during the Extension Phase Part A. (revised per Amendment 19)
- The **OLE PD Analysis Set** is the group of subjects who have sufficient PD data to derive at least 1 PD parameter during the Extension Phase Part A. (revised per Amendment 19)

Similar analysis sets will be defined for the Dosing Regimen substudy. The details will be included in the SAP. (revised per Amendment 17)

EFFICACY ANALYSES

An MMRM will be used to analyze the change from baseline secondary efficacy endpoints. Proportion of amyloid positive subjects over time will be summarized.

An MMRM will also be used to analyze the following exploratory endpoints (revised per Amendment 17):

- Change from baseline in the ADCOMS, CDR-SB, ADAS-Cog score, and MMSE score

For each endpoint at a scheduled visit in the Extension Phase, a 90% 1-sided confidence interval will be constructed to test the null hypothesis that the treatment difference between subjects who took placebo in Core Study and those who took 10 mg/kg biweekly in the Core Study is no more than 50% of the treatment difference at the end of Core Study. If the lower limit of this confidence interval is greater than 0, the null hypothesis is rejected. In addition, comparisons between subjects who took placebo at Core Study and those who took 10 mg/kg biweekly in the Core Study will be performed for each endpoint at scheduled visits in the Extension Phase.

Time to worsening of CDR global scores will be analyzed on the FAS using Cox regression model. Time to worsening of CDR global score is defined as time from the first treatment in the Extension Phase to worsening of the CDR score (ie, the first worsening in 2 consecutive scheduled visits). For subjects whose CDR scores have not worsened by the end of study, the time to worsening of the CDR score will be censored at the date of last CDR assessment for these subjects.

Change from baseline in total hippocampal volume and other biomarkers will be summarized using descriptive statistics at scheduled visits in the Extension Phase.

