Biomarker and efficacy analysis in the Dosing Regimen substudy will also be performed similarly by dosing regimen. The details will be included in SAP. (revised per Amendment 17)

Additional analyses and summaries will be performed as appropriate.

SAFETY ANALYSES

Safety analysis will be performed similarly to the Core Study. All safety analyses will be based on Safety Analysis Set of the Extension Phase. The incidence of TEAE, laboratory test variables, ECG findings, vital signs, brain MRI, ADAs will be summarized using the descriptive statistics. (See [Section 9.7.1.8](#))

Safety analysis in the Dosing Regimen substudy will also be performed similarly by dosing regimen. The details will be included in SAP. (revised per Amendment 17)

EXPLORATORY ANALYSES

No hypothesis testing will be performed for efficacy variables. Descriptive summary statistics will be generated for the efficacy endpoints as follows:

- Continuous variables will be summarized by number, mean, median, maximum, and minimum
- Categorical variables will be summarized by number and percentage

Additional summary/analyses will be performed using appropriate statistical methodologies if deemed necessary.

SAMPLE SIZE RATIONALE

There is no sample size calculation for the Extension Phase Part A. (revised per Amendment 19)

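### The Extension Part A retention test does not say what its confidence interval is for, and for amyloid a between-group test does not measure whether the benefit is maintained

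*Protocol*

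**What the plan says.** The rule appears in Appendix 4 (Statistical Methods, Efficacy Analyses) and in the same words in the Synopsis, Extension Phase Part A efficacy analyses.

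- Scope: "For each endpoint at a scheduled visit in the Extension Phase". The sentence follows the MMRM text for the secondary amyloid PET changes and the exploratory ADCOMS, CDR-SB, ADAS-Cog and MMSE changes.
- Level and purpose: "a 90% 1-sided confidence interval will be constructed to test the null hypothesis".
- Null: the difference between former placebo and former 10 mg/kg biweekly subjects "is no more than 50% of the treatment difference at the end of Core Study".
- Decision: "If the lower limit of this confidence interval is greater than 0, the null hypothesis is rejected".
- Next sentence: in addition, "comparisons between subjects who took placebo at Core Study and those who took 10 mg/kg biweekly in the Core Study will be performed" at the scheduled visits.

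The secondary objective (Section 8) is whether the "treatment benefit in brain amyloid levels (as measured by amyloid PET) at the end of the Core Study will be maintained" over time. Section 9.1.3 states: "All subjects will receive the BAN2401 10 mg/kg biweekly dose", or one of two less frequent regimens for those who enter the Dosing Regimen substudy. Former placebo subjects are therefore all on active drug.

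Under Exploratory Analyses, Appendix 4 also says: "No hypothesis testing will be performed for efficacy variables".

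**The concern.** The null has a margin of half the Core difference, while the decision compares a limit with zero. The only quantity named before the interval is the treatment difference, so an analyst could build the interval for that difference. The rule would then ask whether any difference remains, and could support a claim of more than 50% retention that was never tested.

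For amyloid there is a second problem, which does not depend on how the interval is read. A between-group difference can shrink because early starters lose benefit or because late starters gain it. The objective asks about the first, and the test cannot separate the two. At stake are the Extension's only secondary objective and its exploratory clinical claims.

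**Working it through.** Notation: `D_C` is the placebo versus 10 mg/kg biweekly difference at the end of the Core, `D_E` the same difference at an Extension visit, `z_C` is `D_C` over its standard error, `k` is the Extension/Core standard error ratio, and `ρ` is the correlation of the two estimates.

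**Inputs.** One-sided 90% gives a critical value of 1.2816. Section 7.2.1.2 gives P=0.034 for ADCOMS, P=0.017 for ADAS-Cog and P<0.0001 for amyloid at 18 months. Taken as two-sided (an assumption), these are z = 2.12, 2.39 and at least 3.89. Section 9.7.1.9 gives planned amyloid differences of 0.17 SUVR at 12 months and 0.25 at 18 months, SD 0.4 at 18 months, and 230 subjects over six arms. The Extension has no sample size calculation, so `k` from 1 to 2 is assumed.

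**1. Interval for `D_E − 0.5·D_C`.** The null is `D_E − 0.5·D_C ≤ 0`, so zero is the correct cut-off. Simulation (400,000 draws, `k`=1, `ρ` = 0, 0.5, 0.8) gives rejection at exactly 50% retention of 0.099 to 0.101. The nominal 10% is reproduced.

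**2. Interval for `D_E` alone.** Rejection at exactly 50% retention is Φ(0.5·z_C/k − 1.2816).

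| Endpoint | k=1 | k=2 |
|---|---|---|
| ADCOMS | Φ(1.060 − 1.2816) = 0.41 | Φ(0.530 − 1.2816) = 0.23 |
| ADAS-Cog | Φ(1.194 − 1.2816) = 0.47 | Φ(0.597 − 1.2816) = 0.25 |
| Amyloid (at least) | Φ(1.946 − 1.2816) = 0.75 | Φ(0.973 − 1.2816) = 0.38 |

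With the amyloid planning inputs instead (230/6 ≈ 38 per arm if equal), SE = 0.4·√(2/38.3) = 0.091, z_C = 0.25/0.091 = 2.74, and the `k`=1 figure is 0.53.

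**3. Amyloid catch-up, on either reading.** Start the Extension with a gap of 0.25 SUVR. Let former placebo subjects fall by the planned 0.17 by month 12 and 0.25 by month 18, and early starters by a further `g`. The residual is 0.08 + `g` at month 12 and `g` at month 18. The dosing rationale in Appendix 4 predicts further decline with continued dosing but gives no figure, so `g` from 0 to 0.08 is assumed.

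| g (SUVR) | Month 12, share of 0.25 | Month 18, share of 0.25 |
|---|---|---|
| 0 | 32% | 0% |
| 0.02 | 40% | 8% |
| 0.045 | 50% | 18% |
| 0.08 | 64% | 32% |

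In no row has the early-start group lost anything. This assumes that the gap at Extension entry equals the end-of-Core gap. Month 18 lies between the scheduled Week 53 and Week 105 scans and shows the direction only.

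**4. Sign.** Higher MMSE is better; higher ADCOMS, CDR-SB, ADAS-Cog and SUVR are worse. Under any one subtraction order, benefit is positive for one set and negative for the other. If benefit is `−b`, full retention gives a contrast of −b + 0.5b = −0.5b and total loss gives +0.5b. The rule would then favour rejection when benefit is lost.

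**5. Testing.** One part of Appendix 4 prescribes a test for each endpoint; a later part excludes testing of efficacy variables under Exploratory Analyses. ADCOMS, CDR-SB, ADAS-Cog and MMSE are exploratory endpoints, so both statements apply to them.

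**The case against.** The strongest reply is that an interval built to test a null about half the Core difference is naturally an interval for `D_E − 0.5·D_C`, for which zero is right. The following sentence supports this: it separately plans the comparison for any remaining difference, which would be largely redundant if the first test already did that. This stands. A reader might infer that the plan tests any remaining difference instead of 50% retention. The protocol does not establish that; it only leaves the quantity unnamed. The SAP, which was not at hand, may name it.

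On amyloid, a reader might infer that the difference disappears and the objective would be judged failed. That also goes too far. No Extension amyloid result is given, the Week 13 and Week 27 scans may still show a gap, and continued decline in early starters can keep the 12-month residual above 50%. Nor is this test made the sole criterion: changes from baselines, the change between end of Core and Extension baseline, and the proportion amyloid positive are also listed. What remains is that the prescribed test answers a different question from the objective.

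The sign is partly a convention that an SAP can settle, since no subtraction order is fixed. The exclusion of testing sits under Exploratory Analyses and need not reach secondary amyloid, but it does conflict with the test for the clinical scores.

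**Conclusion.** The concern holds as an ambiguity for the clinical scores and as a mismatch for amyloid. The protocol fixes a null, a level and a decision rule, yet the text admits two tests: one with 10% error and one with about 23% to 75% at exactly 50% retention. The higher figures apply only if the interval is for `D_E` alone, and rest on two-sided P-values from a preliminary analysis and on an assumed `k` of 1 to 2.

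On either reading, the between-group amyloid test does not measure maintenance. Catch-up alone could bring the gap below half of the Core difference by about 12 to 18 months on most of the assumed values. The effect is failure to show retention, not false retention. The single sign rule and the conflicting statements on testing also need correction. Severity is moderate: the Extension's primary objective is safety, the clinical scores are exploratory, and no stated decision depends on this test.

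**What to change.** 1. **Amyloid.** Assess maintenance by the within-group change from end of Core and from Extension baseline, with confidence intervals, in subjects who had 10 mg/kg biweekly in the Core. Keep the between-group difference as descriptive.
2. **Clinical scores.** State that the interval is for `D_E − 0.5·D_C`, with the variance of both estimates and their covariance, for example from one MMRM over Core and Extension visits. Measure both differences from the Core baseline, because change from Extension baseline cannot carry the Core difference forward. Orient each scale so that positive means benefit (reversed for MMSE), and reject if the one-sided 90% lower limit exceeds 0.
3. **Consistency.** Reconcile the exclusion of hypothesis testing under Exploratory Analyses with the test under Efficacy Analyses, and make the same changes in the Synopsis.

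The cost is wording in the protocol and SAP, with no new visits or subjects. The between-group amyloid retention claim is given up. If the literal reading was intended, fewer clinical endpoints may pass: even with full retention and `k`=1, the contrast test for ADCOMS rejects with probability Φ(1.06/√(1.25 − ρ) − 1.2816), which is 0.37 at `ρ`=0 and 0.62 at `ρ`=0.8.

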Hematology, blood chemistry assessments, and urinalysis will be performed at Extension Baseline (Extension Screening Visit), at Extension Phase Weeks 3, 7, 13, 19, 27 (Visits 45, 47, 50, 53, and 57), and every 6 months thereafter. Safety and vMRIs will be performed at Extension Baseline (Extension Screening Visit), at Extension Phase Weeks 9, 13, 27, and every 6 months thereafter.

Clinical assessments will be administered at baseline (Extension Screening Visit) and every 6 months in the morning (whenever possible) in the following order: MMSE, CDR, and the ADAS-Cog.

Florbetapir will be used in the US and flutemetamol will be used in Japan for longitudinal amyloid PET analysis in qualified subjects who participate in the longitudinal imaging substudy (US and Japan only). (revised per Amendment 12) At the Extension Screening Visit, subjects who consented to the longitudinal imaging substudy will be stratified into 2 cohorts based on their treatment allocation during the Core Study. Cohort 1 will have amyloid PET assessments performed at baseline (Extension Screening Visit), Visit 50 (Extension Week 13), Extension Phase Visit 70 [Extension Week 53], and annually thereafter; Cohort 2 will have amyloid PET assessments performed at baseline (Extension Screening Visit), Visit 57 (Extension Week 27), at Extension Phase Visit 70 [Extension Week 53], and annually thereafter. In Japan, those who consented to the longitudinal imaging substudy will only undergo amyloid PET at Extension Phase Visit 70 [Extension Week 53], and annually thereafter. (revised per Amendments 12 and 15)

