Subjects entering the substudy will follow the substudy-specific schedule of assessments (Table 14 and Table 15). Consenting subjects may enter the Dosing Regimen substudy at any time during the Extension Phase Part A after they have completed 18 months in the Extension Phase Part A. Subjects may choose to enter this substudy at any study visit according to their prior biweekly schedule of assessments. (revised per Amendments 17 and 19)

Conduct of the Extension Phase During the Coronavirus Disease 2019 (COVID-19) Pandemic and Other Extenuating Circumstances (revised per Amendment 15)

All study assessment and visit information affected by any extenuating circumstances (eg, the COVID-19 pandemic) will be collected on the case report forms (CRFs). These include but are not limited to any visits or assessments that are missed or not done, any assessments that are performed remotely/offsite or in person/onsite, and any home infusions offered and completed.

During the COVID-19 pandemic and under other extenuating circumstances, every attempt should be made to have Visits 57, 70, 83, 96, 109, 122, 135, 148, 161, End of Study Visit (Visit 174, or Early Termination Visit), and the Follow-Up Visit (visits with clinical assessments) conducted at the study site. However, if this is not feasible under these extenuating circumstances, home infusion at applicable visits may be permitted, only with sponsor approval and only where permitted according to country and local guidelines. During these visits, the clinical assessments, MMSE, CDR, ADAS-Cog14, and C-SSRS, may be conducted remotely via a sponsor-approved telehealth system, following sponsor approval. Where feasible, raters for these assessments should remain unchanged for each subject. Every effort should be made to have the End of Study Visit (Visit 174 or Early Termination Visit) and the Follow-Up CDR assessment performed at the study site.

COVID-19 vaccines and booster shots may be administered during the Extension Phase, but vaccination should be timed such that it will be administered at least 7 days after the previous infusion and at least 7 days before the next infusion. The duration between COVID-19 vaccination and study drug infusions may be reduced to less than 7 days according to the clinical judgement of the investigator, following discussion with the medical monitor. (revised per Amendment 17)

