- Change from end of Core Study in brain amyloid levels as measured by amyloid PET at the baseline of Extension Phase
- Proportion of amyloid positive subjects over time

Exploratory Endpoints

- Change from baselines in ADCOMS, CDR-SB, ADAS-Cog, and MMSE at each visit assessed
- Time to worsening of CDR global scores, eg, the worsening of global CDR score is defined as an increase from baseline by at least 0.5 points on the global CDR scale on 2 consecutive scheduled visits at which global CDR is measured
- Change from baselines in total hippocampal volume and other biomarkers annually in the Extension Phase (revised per Amendment 15)
- Describe the characteristics, comorbidities, treatments, associated costs for subjects with EAD, and study partner burden up to 5 years before study enrollment, for the duration of the Core Study, the duration of the period between the end of the Core Study and the Extension Baseline (if applicable), the duration of the Extension Phase (if applicable), and for up to 3 years after the end of the Core Study or Extension Phase (where applicable) (revised per Amendment 16)

Dosing Regimen Substudy Endpoints (revised per Amendment 17)

- Change from substudy baseline in brain amyloid levels as measured by amyloid PET
- Change from substudy baseline in plasma A β 42/40 ratio and plasma p-tau181
- Change from substudy baseline in ADCOMS, CDR-SB, ADAS-Cog, and MMSE at each visit assessed
- Safety assessments including, but not limited to, AEs, vital signs, ECG, physical examinations, clinical laboratory tests, anti-drug antibody (ADA). MRI assessments of microhemorrhage, vasogenic edema, and other clinically significant abnormalities
- Population PK parameters of BAN2401 in serum, including but not limited, to AUC, C_{av}, Correlation of PK exposure with biomarkers, safety parameters, and efficacy

ANALYSIS SETS

- The **OLE Full Analysis Set (OLE-FAS)** is the group of subjects who receive at least 1 dose of study drug during the Extension Phase and who have a baseline assessment and at least 1 postdose efficacy measurement during the Extension Phase Part A. The baseline assessment is defined as the last measurement prior to first dose of BAN2401 in the Extension Phase Part A. (revised per Amendments 17 and 19)

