Appendix 5 EXTENSION PHASE PART B (revised per Amendment 19)

PRIMARY OBJECTIVE:

To evaluate the long-term safety and tolerability of BAN2401 in subjects with EAD

ELIGIBILITY CRITERIA

Must be currently enrolled in Extension Phase Part A.

STUDY DESIGN AND PLAN

All subjects ongoing in Extension Part A upon implementation of Protocol Amendment 19 will transition to Extension Part B. Extension Phase Part A and Part B combined will continue for up to 60 months (5 years), or until BAN2401 is commercially available for individual subjects at each study site, at which time the subjects will switch to commercial BAN2401, or in the cases where drug is not yet commercially available, treatment will continue until the benefit to risk ratio from treatment with BAN2401 is no longer considered favorable, whichever comes first. Upon transition to Extension Phase Part B, Dosing Regimen substudy subjects will be given the option to remain on their current dosing regimen or transition back to BAN2401 10 mg/kg biweekly infusions.

Subjects in Extension Phase Part B will have procedures and assessments including periodic safety assessments at approximately 6 monthly intervals (± 4 weeks) or as unscheduled assessments, when required.

All infusions will take place in the clinic; however, if approved by the Sponsor and allowable and conducted according to country and local guidelines, subjects will be offered the option of home infusions for approved visits. Home infusions are being implemented as a result of the Coronavirus Disease 2019 (COVID-19) pandemic to allow subjects who cannot visit clinical sites for various reasons to continue receiving treatment. Home infusions will be allowed per Sponsor approval according to country and local guidelines during the COVID-19 pandemic and following its resolution, where permitted.

Subjects will continue in Extension Phase B for a maximum combined (Part A and Part B) open-label treatment duration of up to 60 months (5 years), or until BAN2401 is commercially available for individual subjects at each study site, at which time the subjects will switch to commercial BAN2401, or in the cases where drug is not yet commercially available, treatment will continue until the benefit to risk ratio from treatment with BAN2401 is no longer considered favorable, whichever comes first.

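### Time to CDR-global worsening (Extension Part A): the event is dated at the first of two consecutive scheduled visits but censoring is at the last CDR of any kind, so progression is modestly understated

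*Protocol*

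**What the plan says.** The rules stand in Protocol Appendix 4 (Exploratory Endpoints; Efficacy Analyses) and are repeated in the Section 2 synopsis for Extension Phase Part A.

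- **Event.** Worsening is "an increase from baseline by at least 0.5 points on the global CDR scale on 2 consecutive scheduled visits at which global CDR is measured".
- **Event date.** Time runs from the first Extension treatment to "worsening of the CDR score (ie, the first worsening in 2 consecutive scheduled visits", that is, to the first visit of the confirming pair.
- **Censoring.** For everyone else, "the time to worsening of the CDR score will be censored at the date of last CDR assessment for these subjects". Nothing limits this to scheduled visits, and nothing addresses a worsening seen only at the last CDR.
- **Model and set.** "Time to worsening of CDR global scores will be analyzed on the FAS using Cox regression model".
- **When CDR is done.** "Clinical assessments will be administered at baseline (Extension Screening Visit) and every 6 months". Table 13 also marks CDR under Early Termination, Follow-Up and Unscheduled visits. Appendix 4 (conduct during COVID-19) groups "End of Study Visit (Visit 174, or Early Termination Visit), and the Follow-Up Visit (visits with clinical assessments") with the numbered CDR visits.
- **Move to Part B.** "All subjects ongoing in Extension Part A upon implementation of Protocol Amendment 19 will transition to Extension Part B". Table 16, the Part B schedule, has no CDR row.

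**The concern.** Follow-up should end at the last point at which an event could still have been recorded. Here it ends one assessment later. The event takes the date of the first visit of a pair, so the pair must be complete before an event exists, and a subject's last CDR can never be an event date. The interval leading to that CDR still enters the analysis as event-free time. If the subject did worsen there, the worsening is recorded as its opposite: event-free on the day it was seen.

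The two rules also use different sets of visits. Events are counted "on 2 consecutive scheduled visits at which global CDR is measured", while censoring accepts any CDR. An Early Termination, Follow-Up or Unscheduled CDR may therefore lengthen time at risk without being able to start or confirm an event.

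At stake is a progression rate that reads too low, for the only analysis specified for the objective on time to disease progression. The protocol itself writes both rules, so this is a mismatch in the text and not detail awaiting the SAP.

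**Working it through.** The protocol states no rate, event count, hazard ratio or power for this endpoint, so there is no planned figure to reproduce. The check asks what the two rules do to a known rate.

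**Inputs from the protocol.** CDR every 6 months; at most 60 months, hence at most 10 post-baseline six-monthly CDRs; event dated at the first of two visits; censoring at the last CDR.

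**Assumptions, not in the protocol.** Risk of first worsening per visit *h* = 0.05 to 0.15; worsening sustained once present; exit risk per visit *q* = 0.05 to 0.25.

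**Step 1: a subject with K six-monthly CDRs and no other confirming CDR.** An event needs first worsening at visit K−1 or earlier.

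- Expected events: E = 1 − (1−h)^(K−1)
- Intervals at risk if censored at visit K−1: E/h
- Intervals at risk under the stated rule: E/h + (1−h)^(K−1)

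For h = 0.10, K = 10: (0.9)^9 = 0.387, E = 0.613, and the rate is 0.613/(6.126 + 0.387) = 0.094. For K = 2: 0.10/(1 + 0.9) = 0.053.

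| CDRs (K) | Stated rule, h = 0.10 | Ratio to true rate, h = 0.05 to 0.15 |
|---|---|---|
| 1 | no event possible, 6 months counted | n/a |
| 2 | 0.053 | 0.51–0.54 |
| 3 | 0.070 | 0.68–0.72 |
| 4 | 0.079 | 0.77–0.81 |
| 6 | 0.087 | 0.85–0.89 |
| 10 | 0.094 | 0.92–0.96 |

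Censoring at visit K−1 returns 0.10 in every row from K = 2.

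**Step 2: staggered exit, Early Termination and Follow-Up CDRs not confirming.** At each visit before the tenth, a worsening becomes an event only if the subject stays for one more visit, so the observed per-visit hazard is h(1−q). With h = 0.10 and q = 0.15 it is 0.10 × 0.85 = 0.085. The tenth visit contributes time but no events, which lowers the overall rate to 0.083, about 17% below 0.10. With h = 0.15 it is 0.126 against 0.150. The share of subjects with an unconfirmed worsening at the last CDR is 6.7% and 8.5% respectively. For h = 0.10, 36-month cumulative incidence is 0.451, 0.432, 0.413 and 0.374 at q = 0.05, 0.10, 0.15 and 0.25, against a true 0.469.

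**Step 3: the same, but every leaver has a confirming CDR 3 months after the last six-monthly one.** A worsening at the last six-monthly CDR now counts. The unmatched time shrinks to half an interval per event-free subject. With h = 0.10 and q = 0.15 the rate is 0.093, about 7% low.

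**Step 4: hazard ratio.** Under Step 2 the ratio is multiplied by (1−q₁)/(1−q₀). With equal exit the factor is 1; in simulation 0.80 stayed 0.80 under both censoring rules. With exit of 0.25 versus 0.10 the factor is 0.75/0.90 = 0.83; the simulated null ratio was 0.84. With 0.20 versus 0.15 it is 0.80/0.85 = 0.94. Under Step 3 the null ratio was 0.99 to 1.00 even with exit of 25% versus 10%.

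**The case against.** Several points on the other side are good.

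- **Early Termination and Follow-Up may well be scheduled visits.** Both have columns in Table 13, and Appendix 4 lists them with the numbered CDR visits; the natural contrast is the Unscheduled column. Discontinuing subjects are asked to attend both, and subjects switching to commercial drug undergo the Week 261/Early Termination assessments. This stands and is why Step 3 is needed. It narrows the gap but does not close it: a worsening first seen at the very last CDR still cannot be confirmed, and subjects moved to Part B leave the six-monthly CDR schedule.
- **No progression rate is a named output; the planned analysis is a Cox model.** True, but the same data underlie any event count or incidence curve reported with it.
- **Worsening is taken as permanent.** Confirmation exists to screen out transient change, so the shares of unconfirmed last-CDR worsening above are upper figures.
- **The wording has some give.** The event definition is introduced as an example, and a subject with unconfirmed final worsening is arguably not one whose score has not worsened. If the event were dated at the confirming visit, censoring at the last scheduled CDR would be consistent. The text points to the first visit, however, and the scheduled-versus-any-CDR mismatch would remain.

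A reader might infer that the comparison between Core groups is biased. The documents do not support that. All Extension subjects receive open-label drug, and commercial availability and the Amendment 19 transfer follow site or calendar, not Core arm. Nothing indicates different exit, and with equal exit the ratio is unchanged.

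A reader might also take the named analysis set as the Core FAS, which includes subjects with no Extension time origin. Appendix 4 defines only the OLE-FAS as its full analysis set, and the time origin requires Extension dosing, so this is a shorthand slip.

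**Conclusion.** The mismatch is real and stands in both the synopsis and Appendix 4. It understates progression modestly: about 17% under the assumed 10% risk and 15% exit per visit if Early Termination and Follow-Up CDRs cannot confirm, and about 7% if they can. It is smaller with full 60-month follow-up (4–8% over the assumed risks, even with no confirming CDR after Visit 174) and large only for subjects with few CDRs. All of these figures rest on assumed rates and sustained worsening. The case for change rests on the rate, not on the hazard ratio. Priority is low: the endpoint is exploratory, the extension is open-label and has no sample-size basis, and Appendix 4 says under Exploratory Analyses that efficacy variables will not be formally tested.

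**What to change.** In the synopsis and in Appendix 4, Efficacy Analyses:

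1. State whether CDRs at Early Termination and Follow-Up count as scheduled visits that can confirm worsening. This is the sponsor's choice. Counting Early Termination may allow confirmation soon after the first reading.
2. Censor subjects without confirmed worsening at the last CDR that was followed by another CDR able to confirm it.
3. Add a sensitivity analysis that counts an unconfirmed worsening at the last CDR as an event on that date.
4. Editorially, name the analysis set OLE-FAS.

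No new data are needed; the work is a programmed censoring date and one extra analysis. The price is one CDR interval of follow-up per event-free subject. Subjects with a single post-baseline CDR and no confirming CDR would contribute no time at risk; in the 15%-exit model, 15% of subjects have only one six-monthly CDR.
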